In order to accomplish the study aims, several variables will be measured. Participants will receive an interview, complete questionnaires, undergo a dermatologic exam, have photographic documentation, and provide blood samples at all of the study visits (see attached schedule). Skin biopsies will be optional. The outcome measures also require repeat administration of the SELENA-SLEDAI and the CLASI. Each test requires 5-10 minutes for administration.

Study Visit 1 – Initial Enrollment (Week 1, Before UVA1 Phototherapy):

The patients will have:

- Informed consent
- Full medical/family history and physical examination
- Cutaneous Lupus Erythematosus Disease Area and Severity Index (CLASI) - a measure of cutaneous lupus disease activity
- Systemic Lupus Erythematosus Disease Activity Index with modification from the Safety of Estrogens in Lupus Erythematosus National Assessment (SELENA-SLEDAI) - a measure of systemic lupus disease activity.

- **Sub-Study Procedure:** Optional 4 mm punch biopsies (three; affected-treated, affected-untreated, and unaffected skin) – Patients will have a 4 mm punch biopsy of the active (erythematosus) border of up to two lesions and site-matched (to the affected-treated site) unaffected skin (excluding lesions on the face due to cosmetic concerns). The biopsy will be performed using standard sterile technique. Skin will be closed with a single 3-0 or 4-0 polypropylene or nylon suture. Skin biopsies will be used for DNA/RNA extraction and protein expression studies.
- Clinical photography of involved areas with labeling of ≥ 1 active cutaneous lesion(s) to be covered during phototherapy, referred to as the “shielded cutaneous lupus lesion.”
- 40 cc of blood draws - Blood will be collected from a vein in the subject’s arm for autoantibody titers, complete blood count with differential, BUN and creatinine, DNA/RNA extraction and protein expression studies. The collection will take place during a scheduled research-only clinic visit by a support staff person or an investigator who has been formally trained to conduct venipuncture.
- Skindex-29+3 (modified to include cutaneous lupus-specific questions) – A quality of life survey
- Physician assessments – Study investigators will give a score from 1-10 on overall, activity, and damage aspects of each patient’s skin disease, as well as general health.

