- Phototherapy orientation – The phototherapist will orient all patients to the safety protocols of the unit. Subjects will wear standard UV protective goggles and shield their genitals. A symptom questionnaire assessing symptoms of lupus flare, photosensitivity, and changes in medications will be provided at the initial phototherapy orientation. Participants will be asked to review this at home prior to each UVA1 treatment session. This questionnaire will also be reviewed at each UVA1 treatment session by the phototherapy nursing staff.
- Delivery of UVA1 phototherapy – Patients will receive UVA1 phototherapy according to the protocol stated in Table 1. **The time required to complete UVA1 treatment will be <30 minutes.**

Table 1. UVA1 Phototherapy Standard Protocol
1. Explain treatment to patient.
2. Patients should be treated three times per week.
3. Prior to each treatment session, review lupus flare and photosensitivity questionnaire.
4. Treat whole body except for genitals and “shielded cutaneous lupus lesion.”
5. Goggles should be worn at all times by the patient and the phototherapist.
6. Unit should be a fixed distance from patient. 
 • Whole body – 8-9 inches
7. Patient to apply sunscreen to nipple/areola and cover genitals.
8. Set unit to deliver appropriate dose ($\leq 20 \text{ J/cm}^2$).
9. Dose as follows: 
 a. Initial dose at 6 J/cm^2 b. Second dose at 12 J/cm^2 c. Third dose and all doses thereafter at 20 J/cm^2 in the absence of adverse effects
10. Prior to treatment, always review patient’s medications.

11. Prior to each treatment, inquire for any erythema or symptoms of lupus flare.
12. UVA1 light can induce HSV (cold sores) especially if patient has a personal history. If this occurs, notify the physician for treatment and possible prophylaxis.

Study Visit 2 –UVA1 Treatment Phase (Week 6, After 15 UVA1 Phototherapy Treatments)

The same assessment and procedures will be performed as in Study Visit 1 with the exception of informed consent, phototherapy orientation, and optional skin biopsies.

Study Visits 3 - End of UVA1 Treatment Phase (Week 11, After 30 UVA1 Phototherapy Treatments)

The same assessment and procedures will be performed as in Study Visit 1 with the exception of informed consent and phototherapy orientation.

Study Visit 4 - End of Observation Phase (Week 19, 8 Weeks After UVA1 Phototherapy Treatment Ends)

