7. SOURCES OF RESEARCH MATERIAL

Skin Biopsy

4 mm punch biopsies (three; affected-treated, affected-untreated, and unaffected skin) of up to 15 patients will be performed under local anesthesia by an investigator who has been formally trained to perform a skin biopsy. The biopsies will be performed using standard sterile technique. Skin will be closed with a single 3-0 or 4-0 polypropylene or nylon suture. These biopsies will take place during Study Visits 1 and 3 during a scheduled research-only clinic visit. The investigator will avoid cosmetically sensitive areas such as the face for biopsies, unless the patient permits.

Blood

Approximately 40 cc of blood will be collected from a vein in the subject's arm at the Study Visits during a scheduled research-only clinic visit by a support staff person or an investigator who has been formally trained to conduct venipuncture.

Patient Data

Other data used in the research will be obtained from the subjects' medical records and in-person interviews. The data sought will include the subject's age, gender, race, age of diagnosis, contact information, disease location, presentation and history, associated symptoms, past and current treatments, personal history of autoimmune diseases, family history, and quality of life assessments. At return study visits, subjects will update the investigators on changes to their disease history, associated symptoms, treatments, quality-of-life assessments, and will be assessed for adverse events. At each Study Visit, an investigator will perform a skin examination, obtain severity index scores for cutaneous and systemic lupus (i.e. CLASI, SELENA-SLEDAI), provide physician's assessment of disease activity, and obtain photographs.

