17. RISK/BENEFIT ASSESSMENT

The physical, psychological, social, and/or economic risks to subjects are reasonable in relation to the anticipated benefits to the subjects in relation to the importance of the knowledge that may result.

18. BIostatISTICS

Assuming that the standard deviation is 25%, a sample size of 12 achieves 83% power to detect a difference of 20% with a significance level (alpha) of 0.05 using a one-sided one-sample t-test. However, we are planning to recruit a total of 15 to account for 20% attrition rate due to lost to follow-up and lack of tolerance to UVA1 therapy.

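### No rule decides which active lesion is shielded, how it is matched to the treated lesion, or that Visit 3 biopsies come from the Visit 1 lesions

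*Combined protocol and SAP*

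**What the plan says.** All references are to the combined protocol and SAP.

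- **Shielding.** The opening of section 5 has at least one active lesion covered at treatment and leaves the number open. Study Visit 1 lists "Clinical photography of involved areas with labeling of ≥ 1 active cutaneous lesion(s) to be covered during phototherapy" and gives that lesion a name. Table 1 then excludes the named lesion, with the genitals, from whole-body treatment. This applies to every participant, not only to those who have biopsies.
- **Biopsies.** Section 7 describes "4 mm punch biopsies (three; affected-treated, affected-untreated, and unaffected skin", taken at Visits 1 and 3. They are optional. Section 5 takes the affected samples from the active edge of at most two lesions.
- **Matching.** The only matching rule is for "site-matched (to the affected-treated site) unaffected skin". Nothing matches the untreated lesion to the treated one.
- **Later visits.** For each of Visits 2, 3 and 4, section 5 says "The same assessment and procedures will be performed as in Study Visit 1", with a short list of exceptions.
- **Comparator and analysis.** Section 3 describes an open-label trial and section 6 has no reference therapy. Section 18 contains one test, a one-sample t-test, and does not name its outcome. Section 8 speaks of gene expression before and after treatment. No test of treated against untreated lesions is written anywhere.

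**The concern.** Aim 3 predicts lower numbers of three immune cell types in skin (T, B and plasmacytoid dendritic). A before-after fall in treated skin cannot by itself be credited to UVA1: background lupus drugs continue (sections 3 and 6), treatment falls in autumn and winter, and sun protection is required (section 5). Each of these could change skin disease without UVA1. The untreated affected lesion in the same patient shares all of them, which makes it the only concurrent control for this hypothesis.

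That control works only if the two lesions would have followed the same course without UVA1. With no allocation or matching rule, in a trial where treatment is known to all, the lesions may differ systematically in severity, type or body site. A lesion that starts worse tends to improve more on its own, so a baseline gap passes into the contrast as an apparent effect. Analysis cannot reliably repair this afterwards.

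There is a second gap at Visit 3. The biopsy instruction asks for an active edge, and a treated lesion that has cleared may have none. With nothing tying the Visit 3 samples to the Visit 1 lesions, the sample could move to another lesion, possibly one that did not respond.

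**Working it through.** **1. The plan's own figure.** Inputs from section 18: "Assuming that the standard deviation is 25" per cent; "a sample size of 12 achieves 83% power to detect a difference of 20" per cent; "significance level (alpha) of 0.05 using a one-sided one-sample t-test"; and "we are planning to recruit a total of 15 to account for 20% attrition rate".

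- Standardised effect = 20 / 25 = 0.8.
- Noncentrality = 0.8 × √12 = 2.77, with 11 degrees of freedom.
- One-sided power from the noncentral t distribution = 82.9%, which agrees with 83%.
- Attrition: 12 / (1 − 0.20) = 15, as stated.

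These figures are right and are not in dispute. The calculation has no term for a treated-versus-shielded difference, so nothing below alters it.

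**2. What is and is not fixed in the text.**

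| Feature of the control lesion | Stated? |
|---|---|
| Active at Visit 1 | Yes, section 5 |
| Labelled before phototherapy starts | Yes, section 5, Visit 1 |
| Left out of treatment | Yes, Table 1 |
| Who picks it | No |
| How it is picked | No |
| How many are covered | Left open |
| Matched to the treated lesion | No; only unaffected skin is matched |
| Same lesions biopsied at Visits 1 and 3 | No sentence says so |

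**3. Illustrative size of the bias.** The documents give no lesion-level means, SDs or correlations, so every input here is an assumption. Suppose UVA1 has no effect, both lesions come from a population with the same mean and SD at baseline and Week 11, and each lesion's Week 11 value depends on its own baseline value with correlation r. The expected change of a lesion that starts x SD above the mean is −(1 − r) × x. Subtracting the two lesions gives:

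spurious difference in change = (1 − r) × baseline gap

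| Baseline gap | r = 0.9 | r = 0.7 | r = 0.5 |
|---|---|---|---|
| 0 | 0 | 0 | 0 |
| 0.5 SD | 0.05 SD | 0.15 SD | 0.25 SD |
| 1 SD | 0.10 SD | 0.30 SD | 0.50 SD |

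For example, 0.5 SD × (1 − 0.7) = 0.15 SD. If the treated lesion starts worse, the error favours UVA1; if the shielded lesion starts worse, it counts against UVA1. The gap is the decisive input: at zero there is no such bias for any r.

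The gap must be measured on the biopsy outcome. If lesions are picked on visible severity, the gap in cell counts is smaller to the extent that the two are imperfectly related.

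**4. Effect of randomising.** If chance decides which of two labelled lesions is shielded, the expected gap is 0, so the expected spurious difference is 0 whatever r is. Remaining imbalance is random and falls within the error of a paired comparison.

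**The case against.** Several points on the other side are sound.

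- **The lesion reads as fixed during treatment.** It is named before phototherapy and Table 1 uses that name as a standing exclusion. A reader might infer from the repeat-procedures sentence at Visit 2 that the lesion can be re-chosen at Week 6, so that a control might have had half the course. The documents do not support this. The same sentence governs Weeks 11 and 19, when no sessions remain and labelling a lesion for cover has no purpose. Read literally, it would also repeat UVA1 delivery, which is on the Visit 1 list and not among the exceptions. The appendix lists photographs at the later visits and no re-labelling. The sentence is shorthand for repeating assessments.
- **No selector is named.** A reader might infer that the investigator picks the lesion, and would expose the worse one. The first is plausible, since section 7 has an investigator examine the skin and obtain photographs at each visit, but it is an inference. The second has no support in the text, so the direction of any bias is unknown.
- **The lesions are partly comparable.** Both are active and sampled at the active edge. This narrows the possible gap but does not make it zero.
- **The reach is limited.** The biopsies are optional, no treated-versus-untreated test is specified, and the contrast plays no part in the sample size.

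These points limit the size and reach of the concern. They do not supply the missing rules for choosing and matching the lesion or for carrying the same lesions to Visit 3.

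**Conclusion.** The concern holds as an omission in the design of the lesion-level control. Selection and matching of the shielded lesion are unspecified, and continuity of the biopsied lesions from Visit 1 to Visit 3 is not stated. The contrast of treated with untreated affected skin is therefore open to selection bias in either direction.

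The size cannot be established from the documents. Under the assumptions above it runs from 0 with no baseline gap to 0.5 SD with a 1 SD gap and r = 0.5. The conclusion assumes that the paired biopsies will be used as a control, which the three-sample scheme implies but no analysis text confirms.

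The change is worth making before enrolment because a biased choice cannot be reliably undone later. It bears on an optional sub-study supporting Aim 3 and does not alter the section 18 calculation.

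**What to change.** Add to section 5, Study Visit 1, and repeat in the biopsy paragraph of section 7:

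1. In patients with two suitable active lesions, choose two that are as similar as practicable, then photograph and label both.
2. After labelling and before the first session, use a pre-generated random list to decide which of the two is shielded. Record the result.
3. State that this lesion stays the shielded lesion through session 30, and exempt lesion labelling from the repeat-procedures sentence at later visits.
4. State that the Visit 3 affected biopsies come from the same two lesions, whether or not an active edge remains.
5. Patients with only one suitable lesion stay in the trial but do not contribute to the lesion-level contrast. Report the number of pairs.

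**Cost.** A random list of 15 lines and a few sentences, with no added visit or assessment. The investigator loses the choice of which lesion is exposed. The number of pairs may be small: at most 15 patients are enrolled, biopsies are optional, entry needs a CLASI activity score of only 2, and some patients may have a single suitable lesion. The contrast will then be imprecise, but no longer systematically biased by lesion choice.

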6. TREATMENTS

Investigational Therapy and Reference Therapy

Investigational Agent - low dose UVA1 phototherapy 3 times per week for 10 weeks

Reference therapy - none

Treatment Assignment

After obtaining informed written consent, subjects meeting criteria for inclusion will begin low dose UVA1 phototherapy in escalating doses, as described, up to 20 J/cm².

Concomitant Therapy

Patients will be allowed to continue their concomitant systemic and topical treatments, providing that they meet the inclusion criteria. However, systemic lupus flares will result in removal from the study.

Criteria for Removal from Study

- Missed treatments: If the patient misses ≥ 3 treatments, they will be removed from the study.
- Development of lupus flare, as determined by SELENA-SLEDAI score increase of at least three.
- Intolerance to UVA1 phototherapy despite dose reductions (e.g. induction of UVA1-related skin eruption such as solar urticaria or polymorphic light eruption).

In each case, the principal investigator will assess the patient and determine appropriate therapy outside the auspices of the study. These events will be recorded.

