Treatments will be delivered using Daavlin 4 Series Phototherapy Unit (Daavlin Company, Bryan, Ohio). The unit uses Philips color / 10 phosphor lamps (Phillips International, Eindhoven, The Netherlands) and an acrylic UVB-blocking filter. Photons are emitted at wavelength 340-400 nm. Participants will receive UVA1 treatment three times per week for a total of 10 weeks. An initial test dose of 6 J/cm² will be administered, followed by a test dose at 12 J/cm². Treatments will thereafter be 20 J/cm² for the remainder of the 10-week period. All participants will be required to wear UV protective, opaque goggles. Men will be required to shield their genitalia using an athletic supporter. Additionally, one or more active lesions will be covered during treatment. Treatments will be carried out during the fall and winter months.

An erythema/overdose protocol will be incorporated as follows:

Prevention: Participants will be counseled to avoid further exposure to ultraviolet light. Use of SPF 30 or higher broad spectrum sunscreen, sun avoidance, and sun protection will be required.

Treatment: Participants will be instructed to report all erythema to the study coordinator immediately. Prior to each treatment, trained nurses will interview patients for symptoms of lupus flare. The patients will be assessed by a dermatologist to determine if sunburn erythema or acute cutaneous lupus/LE-related photosensitivity is present. All such episodes will be recorded as adverse events. Patients deemed to have a lupus flare, defined as having a Systemic Lupus Erythematosus Disease Activity Index with modifications from the Safety of Estrogens in Lupus Erythematosus National Assessment (SELENA SLEDAI) score increase of >3, will be withdrawn from the study. Patients deemed to have adverse events related to UVA1 radiation (e.g. erythema) will have a dose reduction to 6 J/cm² for the duration of the study. If these symptoms recur or persist with this dose reduction, the patient will be withdrawn. Phototherapy sessions missed for non-adverse event-related reasons will be rescheduled at the earliest available date.

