11. POTENTIAL RISKS

UVA1 light treatments: There are several potential risks of ultraviolet light exposure:

Short-term risks:

- Marked hyperpigmentation or tanning, erythema, pruritus, photosensitive eruptions, and recrudescence of herpes simplex infection (HSV).
- Flaring of lupus disease, which may include having new skin lesions, increased fatigue, and joint pains.

Long-term risks:

- The most common is aging of the skin: Repeated and prolonged exposure to ultraviolet light induces changes in the skin, which appear as premature aging. These include thinning and wrinkling of the skin in addition to freckling.
- Less common is injury to eyes: Ultraviolet light can injure the subject's eyes. Subjects will be required to wear protective eye shields (goggles) at all times during their UVA1 treatments.
- Rare is skin cancer: Repeated and prolonged exposure to ultraviolet light can increase the subject's risk of skin cancer. This includes exposure from natural sunlight, UVB phototherapy, PUVA or tanning salons. Actinic keratoses (sun-damage spots) can also occur with any long-term exposure to ultraviolet light. Only one case report of UVA1-treated patients developing skin cancers has been reported.¹⁵
- The risk of skin cancer is particularly increased in the genital area, especially in men. Because of this, subjects must shield the genital areas during each treatment

Biopsy: The most common side effects associated with biopsies of the skin are pain at the site, bleeding, bruising at the site, scarring at the site and infection at the site.

Sample of blood: The patient may experience discomfort, bleeding, and/or bruising. The patient may feel dizzy or faint. On a rare occasion, an infection could develop at the site where the blood was collected.

Stress: The patient could experience stress from participating in this kind of research. Knowing that researchers have personal information about them may trouble the patient.

Loss of confidentiality: It is possible that identifiable health information may be accidentally shared and subject confidentiality is lost. Every effort will be made to make sure the subject's information is kept confidential (including the covering of tattoos, birthmarks, etc. in photographs in order to conceal the subject's identity).

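### Removal under Section 6 ends study participation, not only UVA1, and no CLASI is planned at or after it, so patients removed mid-treatment have no end-of-treatment skin outcome

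*Combined protocol and SAP*

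**What the plan says.** Section 6 (Criteria for Removal from Study) lists three grounds.

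- Missed sessions: "Missed treatments: If the patient misses ≥ 3 treatments, they will be removed from the study".
- A lupus flare, defined by a rise in the SELENA-SLEDAI score.
- Intolerance: "Intolerance to UVA1 phototherapy despite dose reductions (e.g. induction of UVA1-related skin eruption such as solar urticaria or polymorphic light eruption").

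For all three, "In each case, the principal investigator will assess the patient and determine appropriate therapy outside the auspices of the study", and the event is recorded. Sections 3, 5 and 12 also describe withdrawal from the study rather than from treatment. Section 5, on adverse events after the reduction to 6 J/cm², says: "If these symptoms recur or persist with this dose reduction, the patient will be withdrawn".

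Checks that can lead to removal are frequent: "Prior to each treatment, trained nurses will interview patients for symptoms of lupus flare" (Section 5). CLASI is not. Section 7 ties it to the study visits. The Appendix table places it at screening and Weeks 1, 6, 11 and 19, and has no early-termination or unscheduled column. The only planned score between baseline and the end of treatment is at Study Visit 2 ("Week 6, After 15 UVA1 Phototherapy Treatments").

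Section 18 gives a one-sided one-sample t-test with 12 patients, and recruits 15 to allow for 20% attrition from loss to follow-up and lack of tolerance to UVA1. It names no analysis set and no rule for missing values.

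**The concern.** The primary aim is the effect of UVA1 on the skin lesions. Two of the three removal grounds may be related to that outcome. Intolerance includes a UVA1-related skin eruption, and Section 11 lists among the risks "Flaring of lupus disease, which may include having new skin lesions, increased fatigue, and joint pains". If patients leave for these reasons and their skin is not scored, the remaining patients may look better than all those treated. With one arm, no control group suffers the same losses, so nothing in the data would reveal the shift.

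Recruiting 15 to keep 12 protects the number of completers. It gives no protection against selective loss. An analysis set can still be chosen late, but a CLASI that was never taken cannot be supplied.

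**Working it through.** **1. The plan's own figure.** Inputs from Section 18: difference 20%, SD 25%, n = 12, one-sided alpha 0.05. The standardised effect is 20/25 = 0.8, the noncentrality is 0.8 × √12 = 2.77, and there are 11 degrees of freedom. Noncentral-t power is 82.9%, which matches the stated 83%. The inflation 12/(1 − 0.20) = 15 is also correct. With all 15 observed and the same assumptions, power is 90.3%.

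**2. Who lacks an end-of-treatment score.** Setting the removal rules beside the Appendix schedule:

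| Time of removal | CLASI available |
|---|---|
| Between Week 1 and Week 6 | Screening and baseline only |
| At the Week 6 visit | Baseline and Week 6 |
| Between Week 6 and Week 11 | Baseline and Week 6; no end-of-treatment score |
| At or after the Week 11 visit | End-of-treatment score intact |

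Removal can be triggered around any of the 30 sessions, so the first and third rows are real possibilities.

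**3. Possible bias in a completers-only result (illustration).** The documents give no removal rate and no link between removal and CLASI change, so both are assumed. Trials of 15 patients were simulated with no true effect and change distributed N(0, 25²). The k patients lowest on a latent variable with correlation r to their CLASI change are removed. A further 3 − k are removed at random, and the remaining 12 are tested at one-sided 5%.

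| Outcome-related losses (of 3) | r = 0.3: error rate (false mean gain) | r = 0.5: error rate (false mean gain) |
|---|---|---|
| 1 | 6.5% (0.9 points) | 7.7% (1.5 points) |
| 2 | 8.0% (1.7 points) | 10.9% (2.9 points) |
| 3 | 9.5% (2.5 points) | 14.5% (4.1 points) |

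At r = 0 the rate is 5.0%. If removed patients tended to do better (r = −0.3), it falls to 3.9% with one outcome-related loss and 2.6% with three.

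**4. Effect of analysing all 15.** Suppose 12 completers average 20%, 3 removed patients average m, and the SD is 25% about each patient's own mean. The overall mean is (12 × 20 + 3m)/15.

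| m | Overall mean | Power, n = 15 |
|---|---|---|
| +20% | 20% | 90% |
| +10% | 18% | 84% |
| 0% | 16% | 73% |
| −20% | 12% | 42% |

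**The case against.** The strongest reply is that the harm depends on an analysis the plan does not state. A reader might infer from the step from 15 to 12 that removed patients will be excluded. Section 18 does not say so: the line sets recruitment, and a Week 6 score could be used for some patients. This stands, and the bias is therefore conditional on a completers-only result. The missing score is not conditional on it.

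A reader might also infer that removed patients are simply those whose lupus skin worsened. The documents support only a partial link. Solar urticaria and polymorphic light eruption are not cutaneous lupus lesions, and Section 4 lists the latter among other photosensitive disorders. The flare criterion is a systemic score. Nothing ties missed sessions to outcome.

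Nor is every removed patient without a score, as the first table under the working shows.

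Removals may be few. Section 5 reschedules sessions missed for reasons other than adverse events, and it reduces the dose to 6 J/cm² before withdrawing a patient for UVA1-related adverse events. Both limit frequency, but neither supplies an outcome once removal occurs. The investigator could take a CLASI at the removal assessment unprompted, but none is planned and the flare criterion needs only SELENA-SLEDAI. Loss to follow-up, the other named cause of attrition, would not be cured by a removal CLASI.

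**Conclusion.** The point holds as a gap in data collection. Following the plan as written loses the end-of-treatment skin outcome of any patient removed before Week 11. If the result then rests on completers, it could overstate the effect.

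The size cannot be determined from the documents. With three losses of which one is outcome-related, the illustration is modest: a false gain of 0.9 to 1.5 points against a 20-point target. The 14.5% error rate needs all three losses to be outcome-related at r = 0.5, and should not be read as the trial's actual error rate. The direction could also reverse.

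The sample-size calculation is correct and is not at issue. The change is worth making because it is cheap and must be made before patients are removed. It falls short of showing that the trial's conclusion would be wrong.

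**What to change.** - Reword Section 6, and the matching text in Sections 3, 5 and 12, so that these criteria end UVA1 treatment only. The safety stop stays exactly as now.
- Take a CLASI at the removal assessment the investigator already makes, before any new lupus therapy starts.
- Invite removed patients to the Week 11 and Week 19 visits.
- Report an analysis of all patients who started UVA1, using the Week 11 CLASI or otherwise the last available one, beside the completers' result. This serves as a sensitivity analysis. Making such a rule the mandatory primary analysis would mix treatment durations and change the question being answered, which is open to debate.

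**Cost.** Protocol wording and one short assessment per removed patient; of CLASI and SELENA-SLEDAI, Section 5 says "Each test requires 5-10 minutes for administration". Return visits may need a small payment change, since Section 16 pays nothing to those who withdraw early for reasons other than adverse effects and does not cover travel. A removal CLASI reflects less than 10 weeks of UVA1 and may capture a transient eruption. The all-treated estimate may be diluted: with three of 15 removed, power is about 84%, 73% or 42% if they average +10%, 0% or −20%.
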